15.3.4 Trial Steering Committee (TSC)

In accordance with the Trial Terms of Reference for the TSC, periodically reviewing safety data and liaising with the DMEC regarding safety issues.

15.3.5 Data Monitoring and Ethics Committee (DMEC)

In accordance with the Trial Terms of Reference for the DMEC, periodically reviewing unblinded overall safety data to determine patterns and trends of events, or to identify safety issues, which would not be apparent on an individual case basis.

16 ECONOMIC EVALUATION

16.1 WITHIN-TRIAL ECONOMIC EVALUATION

The economic evaluation will compare the observed costs and outcomes of the cohort of patients randomised to ELF guided detection and management with those of a cohort of patients randomised to standard care. The perspective of the analysis will be that of the NHS and Personal Social Services.

The primary outcome measure for the within trial economic evaluation is the Quality Adjusted Life Years. Quality of Life weights will be calculated using the EQ-5D™ algorithm³⁷. Life years lived will be obtained from the mortality data collected within the clinical trial at the end of 30 months follow-up.

The primary analysis will consider all direct NHS and Social Care costs incurred by patients randomised to ELF guided detection and management or standard care. Health and social care resource utilisation will be identified using a simple questionnaire completed by the study participants at randomisation and follow-up visits.

Costs and outcomes will be discounted at 3.5% per annum. All costs will be indexed to the trial start year (2009) using the NHS Pay and Prices Index.

The primary result of the economic evaluation will be the incremental cost effectiveness ratio of ELF guided detection and management vs. standard care (ICER). This will be calculated as the difference in the mean cost of the interventions divided by the difference in the mean outcomes.

Parameter uncertainty will be examined using a non-parametric bootstrap simulation³⁸.

Results of the probabilistic sensitivity analysis will be presented as the expected incremental cost effectiveness ratio; a scatter plot on the cost effectiveness plane and as a cost effectiveness acceptability curve (CEAC). The Expected Net Benefit of ELF guided detection and management will be calculated for a range of values of lambda, including £5,000, £15,000, £20,000 and £30,000; reflecting the work of Martin and colleagues³⁹.

16.2 SECONDARY WITHIN-TRIAL ECONOMIC EVALUATION

The secondary within-trial economic evaluation will substitute SF-12v2™ quality of life weights for the EQ-5D™ quality of life weights used in the primary analysis. In all other regards the secondary within-trial economic evaluation will be identical to the primary within-trial economic evaluation.

16.3 LONG TERM ECONOMIC EVALUATION

The clinical trial outcome and resource utilisation data will be used to update the parameters of the pre-existing life time horizon cost effectiveness model. The model will then be used to calculate the expected incremental cost effectiveness ratio ELF guided detection and management, using a lifetime horizon.

Perspective and discounting will be consistent with the methods of primary within trial analysis.

Parameter uncertainty will be examined using Monte Carlo simulation. Results of the probabilistic sensitivity analysis (PSA) will be presented as the expected incremental cost effectiveness ratio; a scatter plot on the cost effectiveness plane and as a cost effectiveness acceptability curve (CEAC). The Expected Net Benefit of ELF guided detection and management will be calculated for a range of values of lambda, including £5,000, £15,000, £20,000 and £30,000; reflecting the work of Martin and colleagues³⁹.

16.4 RESPONSIBILITIES

The management and quality assurance of the health related quality of life and resource utilisation data will be the responsibility of the CTRU.

Implementation of the planned economic analyses will be the responsibility of the Lead Health Economics investigator, [name], of the Academic Unit of Health Economics, University of Leeds.

17 ENDPOINTS

17.1 PRIMARY ENDPOINT

- Time from randomisation to occurrence of first severe complication

Severe complications are defined by:

1. Variceal haemorrhage confirmed by one of the following:
 - a) visualisation through endoscopy
 - b) imaging
 - c) post-mortem
2. Spontaneous bacterial peritonitis:
Ascites confirmed by:
 - a) Imaging and/or
 - b) aspiration*and* infection confirmed by:
 - a) microscopy and/or
 - b) culture
3. Hepatocellular cancer (HCC) beyond the Milan criteria^{* 40, 41}
N.B. For the purposes of the trial cases of HCC falling within the Milan criteria are not regarded as endpoints as they are regarded as treatable.
4. Encephalopathy - grade 3 or 4 defined using the Westhaven criteria (Appendix 1)⁴².
5. Liver-related mortality. Any of the following:
 - a) Any mention of liver disease in part one of the death certificate
 - b) death due to hepatocellular cancer (HCC)
 - c) death due to liver failure
 - d) death due to bleeding from portal hypertension
 - e) death due to hepato-renal syndrome
 - f) death due to sepsis occurring as a result of chronic liver disease
 - g) death due to spontaneous bacterial peritonitis
 - h) death due to encephalopathy

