14.3 FOLLOW-UP FOR PATIENTS AFTER DIAGNOSIS OF CIRRHOSIS

Following ELF or clinical diagnosis of cirrhosis, an authorised member of the research team at site should complete a Cirrhosis CRF and ensure that this is forwarded by fax to the CTRU within 7 days of diagnosis.

Subsequent to diagnosis, patients should attend an initial follow-up assessment at 3 months post diagnosis. All subsequent follow-up visits

should take place every 6 months. , Assessments to be performed are listed in Table 5 (over page). As per the pre-cirrhosis follow up visits a variation of plus or minus one month around the visit due date is permitted.

It is important to note that an individual patient may experience multiple episodes of liver related complications such as bacterial peritonitis, variceal haemorrhage or encephalopathy. Following on from a liver related complication, follow-up should continue on a 6-monthly schedule. If however, patients undergo liver transplantation, further 6 monthly follow-up will cease.

Table 5. Assessments to be performed at Follow-up for patients diagnosed with cirrhosis.

X = compulsory, **Z** = none of these tests are required as part of the ELUCIDATE protocol but if tests are performed as part of routine care please record findings and date of test. **R** = following *confirmed* clinical diagnosis of cirrhosis (according to clinical/biochemical/imaging criteria) patients randomised to the Routine Clinical Monitoring only arm should also have a single ELF test performed as soon after clinical diagnosis is confirmed and has been recorded in patient’s notes. Patients should be requested to refrain from eating a large meal in the 2 hours prior to providing the sample. (Please see section 10.1).

Assessment	Months from diagnosis of cirrhosis					
	0	3	9	15	21	27
History	X	X	X	X	X	X
Exam	X	X	X	X	X	X
ELF	R					
EQ-5D™/SF12v2™ and Health Usage Questionnaire	X	X	X	X	X	X
LFTs	X	X	X	X	X	X
FBC	X	X	X	X	X	X
INR	X	X	X	X	X	X
Glucose	X					
HOMA-IR	Z					
Liver biopsy	Z	Z	Z	Z	Z	Z
Fibroscan	Z		Z		Z	
AFP, USS, CT, MRI, OGD	SEE SECTION 14.3.1					

14.3.1 Compulsory scheduled assessments for the management of liver related complications.

OGD Timing

Timing of initial oesophagogastroduodenoscopy (OGD) following a diagnosis of cirrhosis:

- If the patient underwent OGD within 18 months prior to being diagnosed as cirrhotic, the next OGD should be performed **within 18 months of the previous OGD** unless clinically indicated sooner.

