14.5 CESSATION OF FOLLOW-UP

Cessation of follow-up should only occur under the following circumstances:

- Patient has completed the final follow-up visit at 30 months post-randomisation
- Patient undergoes liver transplantation
- Patient has an episode of severe encephalopathy of (Westhaven criteria 3-4) or otherwise loses capacity to consent
- Patient dies
- Patient withdraws from trial

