18 STATISTICAL CONSIDERATIONS

18.1 SAMPLE SIZE

The RCT is testing the hypothesis that if we monitor patients with chronic liver disease using the ELF score, we will detect liver cirrhosis earlier, and as a result there will be fewer severe complications as well as improvements in other important patient outcomes. We are therefore aiming to show that the incidence of severe complications following cirrhosis is less in the ELF arm.

It was anticipated that the trial would recruit over 24 months with an additional 30 months follow up, and with an additional 39 months long-term follow-up for the primary endpoint of time from randomisation to incidence of first severe complication (taking us to 5 years after the end of the programme grant). Previous studies⁴³ have led us to anticipate that in the standard arm, at 36 months, in patients with an ELF ≥ 9.5 , we will observe severe complications of the order of 3% variceal bleeds, 10% liver decompensation, 1.5% requirement for liver transplantation, 7.5% liver related mortality giving a 22% incidence of potentially preventable undesirable clinical endpoints at 36 months in these patients.

Previous data⁹ has illustrated that approximately 20% of patients will have varices suitable for therapy. Such therapy has a large effect on the progression of these varices (for instance a reduction from 37% progressing to 11%); on the risk of bleeding from these varices (reduced from 30% to 14% in patients with medium to large varices); and on mortality at 36 months (reduced from 7% to 2% over 24 months⁹). Based on this prior data we hypothesise that we could reduce the incidence of the undesirable clinical endpoints of cirrhosis by 40% in the ELF arm.

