19.2.1 Primary endpoint analysis

Incidence and timing of severe complications of cirrhosis will be calculated from the date of randomisation to the occurrence of the first event (severe complication). Cirrhosis is diagnosed either by, having an ELF score ≥ 9.5 in the ELF arm or in the control arm, via standard methods. An 'event' encompasses variceal haemorrhages, spontaneous bacterial peritonitis, unresectable hepatocellular cancer, encephalopathy (grade 3 or 4) and liver

related mortality. Cox regression analysis, adjusting for the minimisation factors (see section 12.2), will be used to compare the differences between the control and ELF arm. Overall survival curves will be calculated using the Kaplan-Meier method, hazard ratios and corresponding 95% confidence intervals will be presented.

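### Liver transplantation counts as a severe complication in the sample size but not in the primary endpoint, so unequal transplant use between arms could bias the hazard ratio in either direction

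*Protocol*

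**What the plan says.** Protocol 17.1 defines the primary endpoint as "Time from randomisation to occurrence of first severe complication" and lists five kinds of severe complication. Transplantation is not one of them. Section 19.2.1 repeats the list for the Cox model: "An 'event' encompasses variceal haemorrhages, spontaneous bacterial peritonitis, unresectable hepatocellular cancer, encephalopathy (grade 3 or 4) and liver"-related mortality. A note in 17.1 deliberately leaves out hepatocellular cancer within the Milan criteria because it is treatable. It says nothing about transplantation for liver failure.

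Section 18.1 describes the same outcome differently. For control patients with ELF of 9.5 or more it states that "we will observe severe complications of the order of" the following size will be seen at 36 months: "3% variceal bleeds, 10% liver decompensation, 1.5% requirement for liver transplantation, 7.5% liver related mortality giving a 22% incidence". That 22% generates the expected events and the power.

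The cessation list in 14.5 includes "Patient undergoes liver transplantation", and 14.3 says "If however, patients undergo liver transplantation, further 6 monthly follow-up will cease". Sections 6.3 and 11 have all consenting patients flagged with routine NHS data, and state no exception for transplanted patients. Section 15.2.1 lists transplantation among the events recorded on the CRFs.

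**The concern.** Take two patients with the same failing liver and no bleed, peritonitis or grade 3–4 encephalopathy so far. One is transplanted at month 20. The other receives no organ and dies of liver failure at month 22. The second is a primary event under item 5 of 17.1. The first is not, and trial visits stop. Grade 3–4 encephalopathy and liver-related death also end follow-up under 14.5, but both are primary events. Transplantation ends follow-up without being one.

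This matters if the arms use transplantation differently. Sites know the allocation, and an ELF score of 9.5 or more starts cirrhosis management in the ELF arm only (10.1, 10.1.2, 12.2). Transplant use could therefore differ as a result of the intervention. The primary hazard ratio would then mix prevention of complications with a difference in how many failing livers were replaced before a listed complication occurred. The secondary endpoint of time from cirrhosis diagnosis to first severe complication (17.2) has the same gap.

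**Working it through.** **1. Inputs.** From 18.1: 22% at 36 months = 3 + 10 + 1.5 + 7.5; 185 high-ELF control patients; 46.4 events among them; 5.1 further control events; about 52 control and 31 ELF-arm events; 24 months of recruitment, 30 or 69 months of follow-up; medians 22.5 and 39.1 years. From 19.2: two-sided 5%. From 6.2: 1:1 allocation.

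**2. Reproducing the plan.** Exponential rate λ = −ln(0.78)/36 = 0.00690 per month. The average event probability over uniform accrual, by Simpson's rule, is 1 − [S(30) + 4S(42) + S(54)]/6 = 0.2508. Then 185 × 0.2508 = 46.4, as stated. With the stated medians (hazard ratio 0.575), the Schoenfeld formula gives:
- 500 per arm, 30 months: 70.1% (stated 70%)
- 500 per arm, 69 months: 92.3% (stated just over 90%)
- 350 per arm, 69 months: 80.9% (stated about 80%)

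The plan's figures therefore do rest on a rate that includes transplantation.

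**3. Share of planned events.** 1.5/22 = 6.8%. That is 46.4 × 1.5/22 = 3.2 events in the high-ELF control group, 52 × 1.5/22 = 3.5 in the control arm, and 83 × 1.5/22 = 5.7 over both arms.

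**4. Effect on the hazard ratio when there is no true difference.** Assume that 22% in each arm reach either a listed event or transplantation by 36 months, that every transplanted patient would otherwise have had a listed event, and that none had one before transplant. The ELF-arm transplant percentages are assumed. Listed events are then 22% minus the transplanted percentage, and the apparent hazard ratio is ln(1 − p_ELF)/ln(1 − p_control). With 1.5% transplanted in control, p_control = 0.205 and −ln(0.795) = 0.2294.

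| ELF-arm transplants | p_ELF | −ln(1 − p_ELF) | Apparent HR |
|---|---|---|---|
| 3% | 0.190 | 0.2107 | 0.92 |
| 2% | 0.200 | 0.2231 | 0.97 |
| 1.5% | 0.205 | 0.2294 | 1.00 |

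A cruder check uses event counts: 52 events per arm including transplants, with 3.5 transplants in control (3.545 unrounded). The ratio of listed events is (52 − k × 3.545)/(52 − 3.545), where k is the ELF-to-control ratio of transplants. It is 0.93 for k = 2, 1.00 for k = 1, 1.04 for k = 0.5 and 1.07 for k = 0. The two methods agree closely at a twofold imbalance (0.92 and 0.93).

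**5. Effect on power if transplantation stays outside the endpoint.** The matching rate is at most 22 − 1.5 = 20.5%. It is an upper limit because the 10% for decompensation is also wider than the items in 17.1. At 20.5% the event probability is 0.2341, and 185 × 0.2341 = 43.3 events. Scaling the 5.1 other events by 0.2341/0.2508 gives 4.8, so control events fall from 51.5 to 48.1. With a 40% reduction in events, Schoenfeld power changes as follows:

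| Per arm, follow-up | 22% | 20.5% |
|---|---|---|
| 500, 30 months | 67.8% | 64.5% |
| 500, 69 months | 90.9% | 88.8% |
| 350, 69 months | 78.7% | 75.8% |

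The 22% column is a little below the figures in step 2 because an exact 40% cut in events (51.5 to 30.9) gives a hazard ratio of 0.587, not 0.575.

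**The case against.** A reader might infer that the design tilts the primary result towards ELF. The protocol does not support that. Its clearest statement that earlier detection leads to more transplantation is in 4.3.1 and concerns hepatocellular cancer. The transplant criteria in 13.1.3 also belong to the cancer pathway, and within-Milan cancer is a reasoned non-event. Section 4.2 stresses the timing of transplantation in general, but nothing predicts more transplants for liver failure in the ELF arm. Section 18.1 points the other way if anything: it hypothesises a 40% reduction in a set of outcomes that includes transplantation, and fewer ELF-arm transplants would bias against ELF.

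A reader might also infer that transplanted patients are lost, or are informatively censored. The protocol does not say that they are censored. Routine-data flagging continues, the final primary analysis comes after five further years (19.1), and a later death with liver disease in part one of the certificate is an event. This stands as a limit on the point. It does not remove it, because the transplant itself is still not counted.

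The size is modest. With 83 events the standard error of the log hazard ratio is about 2/√83 = 0.22, so a shift to 0.97–0.92 is roughly 0.1 to 0.4 of a standard error. Patients who bled or had peritonitis or grade 3–4 encephalopathy before transplant are already counted, so the illustration is towards the upper end for the imbalances assumed.

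Finally, handling of transplantation in the model is often left to the SAP, and 18.1 may be only a proxy taken from previous studies. But the event list, the end of visits and the contrary planning text are all fixed in this protocol, and an SAP cannot make 17.1 and 18.1 agree.

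**Conclusion.** The point holds as an inconsistency that carries a conditional risk of bias. Transplantation is a severe complication for planning and not for analysis, and trial visits end when it happens. Transplantation for liver failure before any listed complication is the unresolved case.

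Bias in the primary hazard ratio requires transplant use to differ between arms, and its direction follows the imbalance: about 0.97–0.92 with 2–3% against 1.5% transplanted, and about 1.04–1.07 with half as many or no ELF-arm transplants. These figures assume no true effect and that every transplanted patient would otherwise have been an event. No transplant rate by arm is given, so neither the direction nor the size can be predicted, and a claim that the result will favour ELF would go beyond the text. The loss of power from the mismatch is only about 2–3 points. The main issue is the event definition, and it is worth settling before the long-term analysis.

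**What to change.** - Reconcile 17.1 and 18.1 on whether transplantation is a severe complication.
- In 19.2.1, pre-specify a sensitivity Cox analysis of the primary endpoint in which liver transplantation is an event on its date, except transplantation for hepatocellular cancer within the Milan criteria, in line with the note in 17.1.
- Tabulate transplants by arm and, where recorded, by indication, beside the primary result.
- The sponsor should confirm that the CRF and the routine data hold the transplant date and indication. Section 15.2.1 has transplants recorded, but nothing in the protocol says that the indication is. Trial visits end by 30 months, so later transplants would have to come from routine data. If the indication is not available, count all transplants in the sensitivity analysis and say so.
- If transplantation stays outside the primary endpoint, restate the planning rate without it (at most 20.5%) and the power that follows.

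The cost is one extra Cox model, one table and a check of data fields. The primary endpoint does not change. The downside is that transplantation partly reflects organ supply and listing decisions, so it suits a sensitivity analysis and not a new primary endpoint.

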17.2 SECONDARY ENDPOINTS

- Time from diagnosis of cirrhosis (by ELF or clinical means) to incidence of first severe complication

* Milan criteria: One lesion less than 5cm, up to 3 lesions smaller than 3cm, no extrahepatic manifestations, no vascular invasion.

- Time from randomisation to diagnosis of cirrhosis by ELF or clinical means (to allow instigation of prophylaxis and screening)
- Process outcomes, namely:
 - treatment with beta-blockers/band ligation (BB/BL) of varices
 - use of endoscopy and ultrasound/AFP tests
 - treatment to normalise LFTs in patients with Hepatitis B and Hepatitis C.
- Detection and timing of complications following cirrhosis, including:
 - Detection of small varices
 - Detection of large varices
 - Incidence of treatable hepatocellular cancer (HCC)
- All causes of mortality
- Specific liver-related morbidity
- Economic evaluation of the ELF test in the early detection of cirrhosis and as such in the initiation of measures to reduce the incidence of severe complications following cirrhosis.
- Quality of Life (QoL)
- Proportion of non-randomised patients (ELF < 8.4) who go on to develop cirrhosis (diagnosed by clinical means) within the follow-up period.

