Eighty out of the first 225 (37%) patients have presented with an ELF >9.49 . We are aiming to recruit 500 patients per arm, so we would expect 185 control arm patients to have an ELF >9.49 . With a 22% incidence rate of severe complications at 36 months, 24 months of recruitment and 30 months of follow up the expected number of events in these 185 patients can be calculated, using the method described by Collett⁴⁴ for sample size estimates based on exponential survival distributions (more details of which can be seen in the SAP). This produces an estimate of 46.4 events in these 185 control arm patients. We would also expect approximately 10% of the remaining 315 control arm patients to progress to cirrhosis on clinical grounds and to subsequently have a similar probability of then developing severe complications. This adds another 5.1 estimated events from this group, giving a total of approximately 52 estimated events in the control arm. We expect to reduce this number by 40% in the ELF arm, giving a total number of estimated events in this arm of 31. The median survival times, assuming negative exponential survival distributions, that would produce these numbers of events for the control and ELF arms with 24 months of recruitment and 30 months of follow up are 22.5 and 39.1 years, respectively. These figures can be used to calculate the power to detect such an effect size, which, with a type I error rate of 5%, gives a figure of 70%. However, if follow-up is continued until five years beyond the end of the programme grant, i.e. 69 months of follow-up rather than 30, the power to detect this effect size increases to just over 90%.

To calculate the power, with these 1000 patients, to detect a difference in the secondary endpoint of numbers of patients encountering severe complications subsequent to being detected with cirrhosis, we also need to estimate the numbers of patients developing cirrhosis in the two arms. We expect approximately 10% of the 315 patients with an ELF score between 8.4 and

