9.49 to develop cirrhosis during the 24 months of recruitment and 36 months of follow-up, which when added to the 185 patients who present with cirrhosis in this arm through having an ELF >9.49 gives a total of 216 patients developing cirrhosis in the ELF arm. In the control arm we expect 185 patients to have an ELF >9.49 and we expect approximately 46 of these to develop severe complications after 24 months of recruitment and 36 months of follow-up and therefore be diagnosed as cirrhotic at that point. We expect a further one third of these 185 patients to be diagnosed as cirrhotic on clinical grounds which adds another 62 patients. In addition we estimate that approximately 10% of the 315 patients with an ELF score between 8.4 and 9.49 will progress to cirrhosis on clinical grounds. This gives a total of 139 patients developing cirrhosis in the control arm. Therefore we are expecting approximately 31/216 patients encountering severe complications in the ELF arm subsequent to development of cirrhosis compared with approximately 52/139 in the control arm, after 24 months of recruitment and 36 months of follow-up. With a type I error rate of 5% we would have >99% power to detect this difference in this secondary endpoint.

The trial as its original size was thus well powered (at least 90% for the primary endpoint from randomisation with an additional 5 years of follow-up) to show that this ELF monitoring policy will be of real clinical benefit.

Following the recommendation by the funding body to close the trial to recruitment, it is anticipated that by the time the resulting protocol amendment is approved and implemented, approximately 700 patients will have been randomised. Based on this, and with follow-up continuing until July 2014, the trial will have adequate statistical power to report on changes in the process of the care which are critical to the prevention of gastro intestinal haemorrhage and Hepatocellular Carcinoma (HCC) in patients with chronic liver disease who are monitored using the ELF test.

The first process of care would be the use of beta-blockers/band ligation (BB/BL) of varices to prevent haemorrhage. The ELUCIDATE trial will not report the major liver events and survival within the period of the Programme. However, recruitment as planned will be sufficient for these analyses if the patients are followed for a further five years and additional funding is being sought to complete this work.

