19.2.2 Secondary endpoint analysis

Incidence and timing of severe complications of cirrhosis from the date of diagnosis of cirrhosis (in clinic, date of clinic visit or blood sample) will be analysed using Cox regression analysis, adjusting for the minimisation factors (see section 12.2), and will be used to compare the differences between the control and ELF arm. Overall survival curves will be calculated using the Kaplan-Meier method, hazard ratios and corresponding 95% confidence intervals will be presented.

Timing to diagnosis of cirrhosis will be calculated from date of randomisation to the date the patient is diagnosed as having cirrhosis (in clinic) either by, in the ELF arm, having an ELF score ≥ 9.5 or in the control arm, via standard methods. Cox regression analysis, adjusting for the minimisation factors (see section 12.2), will be used to compare the differences between the survival curves, which will be calculated using the Kaplan-Meier method. Hazard ratios and corresponding 95% confidence intervals will be presented.

Detection and timing of complications of cirrhosis will be calculated from the date of diagnosis of cirrhosis, to the detection of the first event. An 'event' in this instance encompasses small and large varices, treatable HCC and inoperable HCC. Cox regression analysis, adjusting for the minimisation factors, will be used to compare the differences between the survival curves. Overall survival curves will be calculated using the Kaplan-Meier method, hazard ratios and corresponding 95% confidence intervals will be presented.

Details of all causes of mortality will be collected and documented, specifically including the number of deaths and whether or not they are suspected to be related to any treatments/trial procedures. All liver-related mortalities will be summarised separately.

Details of the economic evaluation of the ELF test are given in Section 16.

For Quality of Life (QoL), we will look at the difference in expected quality-adjusted survival to final follow-up using the Cox proportional hazards model. We will examine the impact of missing data using a Multiple Imputation method.

The proportion of non-randomised patients (where ELF < 8.4 indicating minimal/mild liver fibrosis) who go on to develop cirrhosis during the follow-up period will be summarised in order to assess false-negative rates (see section 6.3).

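### Time from randomisation to diagnosis of cirrhosis counts diagnoses made at a severe complication, so its effect size does not isolate detection in time for prophylaxis

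*Protocol*

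**What the plan says.** Section 17.2 of the protocol gives the endpoint together with its purpose: "Time from randomisation to diagnosis of cirrhosis by ELF or clinical means (to allow instigation of prophylaxis and screening". Aim (a) in section 5.1 is likewise earlier detection so that intervention can come earlier. Section 4.3 describes cirrhosis first recognised at a variceal bleed as the late identification to be avoided.

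Section 19.2.2 sets the analysis: "Timing to diagnosis of cirrhosis will be calculated from date of randomisation to the date the patient is diagnosed as having cirrhosis". The means are an ELF score of 9.5 or more in the ELF arm and standard methods in the control arm, with Cox regression adjusted for the minimisation factors and Kaplan-Meier curves. Neither section separates a diagnosis made before a severe complication from one prompted by it.

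Section 18.1 shows that the second kind is expected. Of the 185 control patients with ELF above 9.49, about 46 are expected to have a severe complication "and therefore be diagnosed as cirrhotic at that point". They are included in the planned total of 139 control patients with cirrhosis.

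**The concern.** The purpose attached to the endpoint needs a diagnosis early enough to act on, but the event is a diagnosis by any route at any time. A first variceal bleed in an undiagnosed control patient is a primary-endpoint event under section 17.1 and, on the planning logic of section 18.1, also a diagnosis on the same date. One occurrence can therefore count as a failure in one analysis and a detection in another.

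The trial's hypothesis is that earlier detection leads to fewer severe complications. The quantity that bears on it is how many patients in each arm are diagnosed before a complication, and how many reach one undiagnosed. A single all-route time to diagnosis merges the two. Early closure sharpens this: section 18.1 says major liver events will not be reported within the programme period, so the diagnosis result may appear before the complication result that would help readers interpret it.

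**Working it through.** **Inputs (protocol section 18.1, 1000-patient plan, 500 per arm)**
- Control patients: "we would expect 185 control arm patients to have an ELF >9.49".
- Event rate in this group: 22% at 36 months.
- Timing: "With a 22% incidence rate of severe complications at 36 months, 24 months of recruitment and 30 months of follow up".
- A further third of the 185 diagnosed on clinical grounds (62).
- 10% of the 315 patients with ELF 8.4 to 9.49 diagnosed during follow-up in each arm (31 in the protocol's sums).
- ELF-arm total: 185 + 31 = 216.

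**Reproducing the 46.** Exponential survival with λ = −ln(0.78)/36 = 0.00690 per month and uniform accrual over 24 months. Expected events = 185 × {1 − [S(30) + 4S(42) + S(54)]/6} = 185 × {1 − [0.813 + 4(0.748) + 0.689]/6} = 46.4. This matches the protocol: "This produces an estimate of 46.4 events in these 185 control arm patients".

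**Reproducing the 139.** 46 + 62 + 31 = 139, as stated.

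**Complication-led share.** 46/139 = 33.1% of all planned control diagnoses. Among control diagnoses with ELF above 9.49 it is 46/(46 + 62) = 42.6%.

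**Follow-up mismatch.** Section 18.1 later attaches the 46 to 36 months of follow-up, but 46.4 is the 30-month figure. With S(36), S(48) and S(60), the same formula gives 52.0 events. The total becomes 52 + 62 + 31 = 145 and the share 52/145 = 35.9%. The count diagnosed before a complication is 93 in both cases.

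**Effect on the planned contrast**

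| | Control | ELF | Ratio |
|---|---|---|---|
| Diagnosis by any route | 139/500 = 27.8% | 216/500 = 43.2% | 216/139 = 1.55 |
| Diagnosis before a complication | 93/500 = 18.6% | 216/500 = 43.2% | 216/93 = 2.32 |

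The second row assumes no complication-led diagnoses in the ELF arm. At the other extreme, if all 31 ELF-arm patients diagnosed during follow-up were complication-led, the ELF figure would be 185/500 = 37.0% and the ratio 185/93 = 1.99.

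**Approximate hazard-ratio scale.** Under constant hazards, any route gives ln(1 − 0.432)/ln(1 − 0.278) = 1.74. Diagnosis before a complication gives ln(1 − 0.432)/ln(1 − 0.186) = 2.75. This is only a guide, because 185 of the 216 ELF-arm diagnoses (86%) fall at randomisation.

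**Power (two proportions, two-sided 5%).** At 500 per arm, 27.8% v 43.2% gives 99.9% and 18.6% v 43.2% gives more than 99.9%. At 350 per arm the figures are 99.0% and more than 99.9%.

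**The 700-patient plan.** Section 18.1 expects control diagnosis in under 10% by July 2014, so fewer than 35 of 350, with no split by route. If the planning shares carried over, 33.1% to 35.9% of 35 would be 11.6 to 12.6 patients. That is an assumption, not a figure from the protocol.

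**The case against.** Several points against the concern have force.

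- A reader might infer that a diagnosis at a bleed scores the same as one at randomisation. It does not. The analysis is of time to event: most planned ELF-arm diagnoses are notified at randomisation, while a complication-led control diagnosis enters as a late event. This stands. Late recognition is already penalised, although it still counts as a detection.
- A reader might infer that a third of control diagnoses in the trial as now planned will be complication-led. The protocol does not support that. The 46 and 139 come from the 1000-patient text, where 139 is the denominator for a different secondary endpoint (complications after diagnosis).
- A reader might infer that patients who die undiagnosed are simply censored. Section 19.2.2 gives no rule, and that detail may properly sit in the SAP.
- The endpoint definition itself never says that a complication is a diagnosis. Section 12.4 refers to examination, laboratory tests and imaging, and the analysis text runs "to the date the patient is diagnosed as having cirrhosis (in clinic", which leaves an emergency presentation unclear. The complication-led reading rests on section 18.1 and on the absence of any exclusion.
- Prophylaxis and surveillance can still follow a complication in survivors (section 13), so the stated purpose is not flatly contradicted.
- The primary endpoint counts complications whether or not cirrhosis was already diagnosed, and the process outcomes measure prophylaxis and surveillance directly. Nothing is concealed for good.

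These points limit the size and certainty of the problem. They do not remove it: the plan expects diagnoses at complications, and the event definition does not set them apart.

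**Conclusion.** The concern holds as a point of interpretation and effect size. In the 1000-patient planning figures, about 33% of control diagnoses (36% with 36 months of follow-up applied consistently) occur at the severe complication itself. Control diagnosis before a complication is 18.6% rather than 27.8%, and the ratio to the ELF arm is 2.32 rather than 1.55, or 1.99 under the extreme ELF-arm assumption.

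It would be tempting to conclude that the endpoint could produce a false claim for ELF. The direction is the opposite: complication-led diagnoses credit the control arm, so the contrast is conservative and power is barely affected. The conclusion rests on the planning counts in section 18.1, on few complication-led diagnoses in the ELF arm, and on section 19.2.2 counting every diagnosis date. How many such diagnoses to expect with about 700 patients is unknown.

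**What to change.** In sections 17.2 and 19.2.2:
- Define the event as a diagnosis of cirrhosis made before any severe complication. State that a diagnosis dated on or after the first severe complication does not qualify.
- Treat a severe complication or death without prior diagnosis as a competing event.
- Report by arm the cumulative incidence of (i) diagnosis before a complication and (ii) complication or death before diagnosis.
- Keep all-route time to diagnosis as a sensitivity analysis.

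The cost is wording, slightly more analysis and a second version of one secondary endpoint. No new data are needed: diagnosis is reported on the Cirrhosis CRF (section 14.3), complications are recorded on the CRFs (section 15.2.1), and deaths are collected (sections 11 and 19.2.2).
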